### 9.3 ANALYSES SETS

The analysis sets will consist of experimental units as defined below:

• Full Analysis Set (FAS): All participants who completed at least one recall-based assessment (that is, at least one non-daily assessment) will contribute to the FAS. Upon review of the data, additional observations may be excluded from the FAS, based on data cleaning rules specified in the psychometric analysis plan (PAP).

### 9.4 STATISTICAL ANALYSES

In general, continuous variables will be summarized by number of participants, mean, standard deviation, median, minimum, and maximum values. Categorical variables will be summarized by number and percentage of participants responding to each discrete category.

### 9.5 PSYCHOMETRIC ANALYSES

A PAP will be developed and finalized before database lock and will describe the participant populations to be included in the analyses, and procedures for accounting for missing or unused data. The main features of the planned psychometric analyses of the target outcomes/endpoints are, for each measure of both the MiCOAS-DA and recall-based measures:

- Descriptive Statistics of sample
- Item-Level Descriptive Statistics
- Psychometric Analyses
  - Dimensionality/Item Factor Analytic Modeling
  - Item Response Theory Analyses
- Reliability
  - Internal Consistency Reliability
  - Test-retest Reliability
- Validation Analyses
  - Convergent/Discriminant Validity
  - Known Groups Analyses
  - Ability to Detect Change
  - Meaningful Within-person Change Threshold Estimates

### 10 SUPPORTING DOCUMENTATION AND OPERATIONAL CONSIDERATIONS

### 10.1 REGULATORY AND ETHICAL CONSIDERATIONS

This study will be conducted in accordance with the protocol and with the following:

- Consensus ethical principles derived from international guidelines including the Declaration of Helsinki and Council for International Organizations of Medical Sciences International Ethical Guidelines
- Applicable International Council for Harmonisation (ICH)/International Organization for Standardization good clinical practice guidelines
- Applicable laws and regulations

The protocol, protocol amendments, ICF, investigator's brochure, and other relevant documents (e.g., advertisements) must be submitted to an institutional review board (IRB)/Independent ethics committee (IEC) by the investigator and reviewed and approved by the IRB/IEC before the study is initiated.

Any amendments to the protocol will require IRB/IEC approval before implementation of changes made to the study design, except for changes necessary to eliminate an immediate hazard to study participants.

The investigator will be responsible for the following:

- Providing written summaries of the status of the study to the IRB/IEC annually or more frequently in accordance with the requirements, policies, and procedures established by the IRB/IEC
- Notifying the IRB/IEC of serious adverse events (SAEs) or other significant safety findings as required by IRB/IEC procedures. Given the observational nature of this study, however, such SAEs or safety findings are unlikely.
- Providing oversight of the overall conduct of the study at the site and adherence to requirements of applicable local regulations, for example 21 CFR, ICH guidelines, the IRB/IEC, and European regulation 536/2014 for clinical studies (if applicable)

### 10.2 FINANCIAL DISCLOSURES

Investigators and sub-investigators will provide sufficient, accurate financial information as necessary to submit complete and accurate financial certification or disclosure statements to the appropriate regulatory authorities. Investigators are responsible for providing information on financial interests during the course of the study and for 1 year after completion of the study. All disseminations of results will include the required FDA language regarding grant funding and the current amount of the award based on the most recent notice of award at the time of publication/presentation.

### 10.3 INFORMED CONSENT PROCESS

If contacted at the email addresses/phone numbers provided on the electronic ICF, the investigator or his/her representative will explain the nature of the study to the participant or his/her legally authorized representative and answer all questions regarding the study.

Participants must be informed that their participation is voluntary. Participants will be required to sign a statement of informed consent that meets the requirements of 21 CFR 50, local regulations, ICH guidelines, Health Insurance Portability and Accountability Act of 1996 requirements, where applicable, and the IRB/IEC or study center.

The study record must include a statement that written informed consent was obtained before the participant was enrolled in the study and the date the electronically signed consent was obtained.

Participants must be re-consented to the most current version of the ICF(s) during their participation in the study.

A copy of the ICF(s) must be provided to the participant or the participant's legally authorized representative.

### 10.4 DATA PROTECTION

Participants will be assigned a unique identifier. Any participant records or datasets that are provided to sponsor staff for analysis will contain the identifier only; participant names or any information which would make the participant identifiable will not be provided to study personnel unless required.

The participant must be informed that his/her personal study-related data will be used by the sponsor in accordance with local data protection law. The level of disclosure must also be explained to the participant.

# 10.5 DATA QUALITY ASSURANCE

The Sponsor will permit study-related monitoring (if needed), audits, IRB/IEC review, and regulatory agency inspections and provide direct access to source data documents.

The sponsor or designee is responsible for the data management of this study including quality checking of the data.

Records and documents, including electronically signed ICFs, pertaining to the conduct of this study must be retained by the Sponsor on secure, encrypted servers. Record retention and destruction will be consistent with Sponsor standard operating procedures.

### 10.5.1 Data Capture System

An electronic data capture (EDC) system will be used in this study for the collection of study data. All study data will be directly recorded by the participant, into the EDC system. The electronic data will serve as the source documentation and the investigator does not maintain a separate, written or electronic record of these data.

Data collected via the sponsor-provided data capture system(s) will be stored by the sponsor. The investigator will have continuous access to the data during the study and until decommissioning of the study within the data capture system(s).

### 10.6 SOURCE DOCUMENTS

Definition of what constitutes source data can be found in Section 4.0 of ICH E6, Good Clinical Practice: Consolidated Guidance and must follow ALCOA, i.e., records must be attributable, legible, contemporaneous, original, and accurate.

Source documents provide evidence for the existence of the participant and substantiate the integrity of the data collected. All source material is provided by the subjects directly into the EDC system.

### 10.7 PUBLICATION POLICY

VPG as the sponsor has proprietary interest in this study. Authorship will be established prior to the writing of the manuscript.

Authorship will be determined by mutual agreement and in line with International Committee of Medical Journal Editors authorship requirements.

### 10.8 COMPLIANCE WITH PROTOCOL

The investigator is responsible for compliance with the protocol. Protocol deviations will be discussed with the PIs upon identification. Significant protocol deviations will be reported to the IRB/IEC according to the IRB/IEC's reporting requirements.

# 12 APPENDIX A - MICOAS QUANT1 I/E SCREENER

The following questions ask about you. Your answers will be used to see whether you are eligible to participate in a study about people's experience with migraine.

Please read each question carefully.
Check the box next to your answer for each question.

 
Are you an employee of the Food and Drug Administration, Albert Einstein College of Medicine, o Vector Psychometric Group?
 
Yes
 
No
 

2. Has a doctor or other health care professional ever told you that you have migraine?

Yes

No

 
3. How old are you?
 
Less than 18 years old
 
18 to 75 years old
 
76 years old or more
 

4. Do you currently live in the United States?

☐ Yes

☐ No

5. Are you able to tell the difference between a day with migraine and days with other types of headaches?

Yes

No

 
6. Over the last 3 months, how many migraine headache days have you typically had per month?
 
□ 0-3 headache days per month
 
□ 9-14 headache days per month
 
□ 15-20 headache days per month
 
□ 21-26 headache days per month
 
□ More than 26 headache days per month
 

7. Please rate how frequently you experience the following symptoms when you have a headache:

	Never	Rarely	Less than Half the Time	Half the Time or More
The pain is worse on one side				
The pain is pounding, pulsating, or throbbing				
The pain has moderate or severe intensity				
The pain is made worse by routine activities such as walking or climbing stairs				
You feel nauseated or sick to your stomach or vomit (throw up)				
Light bothers you (more than when you do not have a headache)				
Sound bothers you (more than when you do not have a headache)				
Your skin is sensitive to things that are usually not painful such as taking a shower, laying your head on a pillow, brushing your hair or wearing an earring.				

8. Has a doctor or other health care profess	ional ever told you that you have any of the following?
(Please check all that apply)	
☐ Multiple sclerosis	
$\square$ Traumatic brain injury or spinal c	ord injury
☐ Schizophrenia	
☐ Bi-polar disorder	( ) *
☐ Alzheimer's disease or dementia	
☐ Epilepsy	
☐ Stroke	
☐ Cognitive impairment	
☐ None of the above	
	sed an opioid (e.g., Percocet or OxyContin) or barbiturate
, , ,	ther for your migraine or for something else?
□ 0 -2 days	
☐ 3-4 days	
☐ 5-7 days	
☐ 8-10 days	
☐ More than 10 days	
6 1 11 11 5 11	611 4 15 16
	h as to read a newspaper or fill out a medical form on your
own?	
☐ Yes	
□ No	

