- Cohort 1: Total study duration of 8 weeks (2 months) and participants will complete MiCOAS-DA daily for the entire study length. Participants will also complete the MiCOAS-14 and key reference patient reported outcome measures (PROMs) throughout the 8-week study duration (e.g., weekly, biweekly, or monthly depending on the recall period of the PROM).

- Cohort 2: Total study duration of 4 weeks (1 month) and participants will complete MiCOAS-DA daily for the entirety of Month 1 (Weeks 1-4). Participants will also complete the MiCOAS-14 and key reference PROMs throughout the 4-week study duration (e.g., weekly, biweekly, or monthly depending on the recall period of the PROM).
- Cohort 3: Total study duration of 4 weeks (1 month) and participants will complete MiCOAS-DA daily for the entirety of Month 1 (Weeks 1-4). Participants will also complete the MiCOAS-7 and relevant reference PROMs throughout the 4-week study duration (e.g., weekly or monthly depending on the recall period of the PROM).

Cohorts were included in the design to allow for the collection of all necessary data for psychometric and validation analyses while limiting the burden to respondents.

**Population:** Adult patients with a self-reported medical diagnosis of migraine confirmed by a positive diagnosis on the 3-item ID Migraine screen (Lipton et al., 2003).

**Variables:** A range of variables will be collected. The primary focus will be on variables relating to the MiCOAS item sets (MiCOAS-DA, -7, and -14) and the reference PROMs used for validation, but data collection also includes:

- Demographics
- Clinical background characteristics (e.g., medications, brief medical history, comorbidities)
- Migraine-related characteristics (e.g., migraine history, headache days)
- Preventive and acute migraine/headache medication use
- Reference general headache-related PROMs

Data Source/Data Collection: Data will be collected electronically via the flexCOA eCOA system.

**Study Size:** Enrollment of approximately 1200 eligible participants is planned to achieve as many complete records as possible, with a target of 1000 participants who complete assessments throughout the full duration of their assigned study duration.

Study Duration: Minimum of 4 weeks, maximum of 8 weeks

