### 6 STUDY POPULATION

The study population consists of people living with migraine who have a self-reported medical diagnosis of such.

An individual will be initially eligible for the study if all inclusion criteria are met and none of the exclusion criteria are met. Final determination of eligibility will be based on a person's self-report in responding to a set of screening questions, including the 7-item American Migraine Prevalence and Prevention/American Migraine Study (AMPP/AMS) diagnostic module for migraine which has been previously validated (e.g., Lipton et al., 2001).

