### 6.1 INCLUSION CRITERIA

To be eligible for inclusion in the study, at the time of screening, a person must:

- Be currently living in the US
- Be between 18 and 75 years of age
  - Note, age of consent is over 18 in some U.S. states. Age of eligibility within each state will be modified, as needed, to be consistent with state laws ensuring all subjects may legally consent.
- Report being diagnosed with migraine by a healthcare professional
- Report experiencing 4-26 headache days per month over the last 3 months covering the typical range of eligibility in clinical trials.
- Report being able to distinguish between a day with migraine and other types of headache days
- Meet the criteria for migraine on the AMPP/AMS diagnostic module (Lipton et al., 2001; see item 7 of Appendix A):
  - Respondent meets criteria for migraine if:
    - 2/4 pain features (items 1-4) with score of ≥3
    - AND nausea (item 5) score ≥3 OR BOTH photophobia (item 6) AND phonophobia (item 7) score ≥3.
- Be comfortable reading and speaking in English (i.e., ability to read, write, speak, and understand English well enough to complete informed consent process and take part in the interview).
- Be able to provide informed consent to participate in the study and complete the informed consent documentation

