### 6.2 EXCLUSION CRITERIA

An individual reporting any of the following at the time of screening will be excluded from this study:

- Self-reported of any other clinically significant health condition that might interfere with the person's ability to provide non-confounded descriptions of their experience with migraine-related cognitive, psychosocial, or physical impacts. These include:
  - Multiple sclerosis
  - Traumatic brain injury or spinal cord injury
  - Schizophrenia
  - Bi-polar disorder
  - Alzheimer's disease or dementia
  - Epilepsy
  - Stroke
  - Cognitive impairment
- Self-reported use of opioids or barbiturates more than 4 days during the past 30 days
- Self-reported alcohol or drug abuse over the past 3 months
- Is currently participating in a clinical trial related to migraine
- Is an employee or family member of an employee of FDA, Vector Psychometric Group, LLC, or the Albert Einstein College of Medicine.
- Is unwilling to complete a daily assessment, taking about 5 minutes per day, every day of the study.
- Is unwilling to complete other assessments, taking about 45 minutes per assessment, multiple times throughout the study.

A copy of the Inclusion/Exclusion criteria items can be found in Appendix A.

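### Screener item 6 asks for migraine headache days while the Section 6.1 criterion counts headache days, so read literally it can reject people who qualify and admit people above the cap

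*Protocol*

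**What the plan says.** **Frequency criterion.** Protocol Section 6.1 requires a candidate to "Report experiencing 4-26 headache days per month over the last 3 months covering the typical range of eligibility in clinical trials".

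**Frequency item.** Appendix A, item 6 asks "Over the last 3 months, how many migraine headache days have you typically had per month". Its answer options use the other term, for example "21-26 headache days per month". No other visible screener item asks about frequency.

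**The two terms elsewhere.** Section 6.1 has a separate criterion, "Report being able to distinguish between a day with migraine and other types of headache days", and screener item 5 puts that question just before item 6. Section 8.1.10 defines a migraine day as a headache day that meets further conditions, or a day on which acute migraine medication was used for head pain. Appendix B, item 3 asks enrolled participants for days in the last 4 weeks with any headache, migraine counted in.

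**How eligibility is decided.** Section 6 rests the final determination on self-reported answers to the screening questions. Section 6.4 does not allow screen failures to be rescreened.

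**Two neighbouring texts.** The synopsis (Section 2.1, Population) has the diagnosis "confirmed by a positive diagnosis on the 3-item ID Migraine screen". Section 6 relies on screening questions "including the 7-item American Migraine Prevalence and Prevention/American Migraine Study (AMPP/AMS) diagnostic module for migraine", Section 6.1 makes that module an inclusion criterion, and screener item 7 carries it. Section 6.2 excludes anyone who "Is an employee or family member of an employee of FDA" or of the two partner organisations; screener item 1 asks only whether the respondent is an employee.

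**The concern.** A criterion written in one quantity is applied by a question about another, and the question disagrees with its own answer labels. A respondent who has just confirmed, in item 5, that they can tell migraine days from other headache days has reason to answer item 6 with the smaller count. Both limits of the 4-26 range are then applied to the wrong variable.

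The enrolled frequency range defines the population that the item calibration, reliability and validity results describe. Section 6.1 justifies the range by reference to clinical trial eligibility. If the range applied differs from the range written, that description is inaccurate at both ends, and the people lost at the lower end cannot return.

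**Working it through.** The protocol states no figure that depends on this point, so there is nothing to reproduce. The check compares the two rules directly.

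**Inputs**
- H = headache days per month, the Section 6.1 quantity. Rule as written: 4 ≤ H ≤ 26.
- M = migraine headache days per month, the item 6 stem. Rule as asked, read literally: 4 ≤ M ≤ 26.
- A migraine headache day is also a headache day, so M ≤ H.
- Assumption: a 30-day month, so 0 ≤ M ≤ H ≤ 30.

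**Step 1. Possible pairs.** For each H there are H + 1 values of M. Summed over H = 0 to 30 this is 31 × 32 / 2 = 496 pairs.

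**Step 2. Meets Section 6.1 but fails item 6.** H is 4-26 (23 values). M must lie outside 4-26; it cannot exceed 26 because M ≤ H, so M is 0-3 (4 values, all possible when H ≥ 4). That is 23 × 4 = 92 pairs. Example: 8 headache days, 3 of them migraine.

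**Step 3. Fails Section 6.1 but passes item 6.** M is 4-26 (23 values), which forces H ≥ 4, so H can fail only by exceeding 26: H is 27-30 (4 values). That is 4 × 23 = 92 pairs. Example: 30 headache days, 12 of them migraine.

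**Step 4. Agreement.** The rules agree on the remaining 496 − 92 − 92 = 312 pairs.

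The counts are not weighted by how common each pair is. They show that error can run in two directions and where it falls; they are not a rate. A rate needs the joint distribution of H and M among people who reach the screener, which the protocol does not give.

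**Diagnostic screen.** Section 6.1 scores four pain features, nausea, and sensitivity to light and to sound. Screener item 7 contains these seven rows plus a skin-sensitivity row that Section 6.1 does not score. The screener therefore uses the module that Sections 6 and 6.1 require, and the synopsis is the text out of line. The 2003 source that the synopsis cites is also absent from the reference list in Section 11.

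**Employees.** Section 6.2 covers employees and their family members; item 1 covers employees only. This has no bearing on the frequency range.

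**The case against.** **The labels may rescue the item.** The visible answers are in headache days, and the visible cut points (0-3, 21-26, more than 26) fit the 4-26 criterion. A respondent may answer in headache days despite the stem. This stands: misclassification is possible, not shown. It does not clear the item, because a stem and labels that disagree leave the quantity undefined.

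**Errors among those admitted can be seen.** Appendix B, items 3 and 4 record headache days and headache-free days in the last 4 weeks, and Section 7.2 lets the investigator withdraw a participant for administrative reasons. The enrolled headache frequency can therefore be reported, although over 4 weeks and not 3 months. This stands for people wrongly admitted. It does nothing for people wrongly screened out, who never complete Appendix B.

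**Stronger readings that the documents do not support.**
- A reader might infer that the wrong people will be enrolled, or that score distributions will shift by some amount. No figure in the protocol supports a rate or a shift.
- A reader might infer that the 3-item screen in the synopsis changes who gets in. It does not act through the screener, because item 7 carries the symptoms that Section 6.1 scores.
- A reader might infer that the screener as a whole departs from the criteria. The items on diagnosis, age, residence, telling migraine days apart, listed conditions, opioid or barbiturate days and current trial enrolment follow Sections 6.1 and 6.2.
- A reader might infer that item 6 has no 4-8 day answer, since none is visible in the text at hand. Other items on the same pages are visibly broken or cut short, so this may be a loss in reading the PDF and carries no weight here.

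**Conclusion.** The inconsistency is real and lies in the text itself: Section 6.1 counts headache days, the item 6 stem counts migraine headache days, and the item 6 labels revert to headache days. Read literally, item 6 can reject people with 4-26 headache days and 0-3 migraine days, finally because of Section 6.4, and can admit people with more than 26 headache days and 4-26 migraine days.

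The direction rests only on M ≤ H and a literal reading of the stem; the 30-day month affects only the pair counts. The share of candidates affected cannot be computed from the documents. Nor do they settle whether the criterion or the stem carries the intended quantity, so the finding is that they must be reconciled. It is worth correcting because eligibility rests on self-report and the edit is small. The synopsis and family-member mismatches are consistency errors and add nothing to the frequency problem.

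**What to change.** **Main change.** Decide which quantity is meant and use it in the item 6 stem, the item 6 answer labels and Section 6.1.
- If Section 6.1 stands, reword the stem to ask for days per month with any headache, migraine included, following the approach of Appendix B, item 3, and keep the headache-day labels.
- If migraine days were intended, restate Section 6.1 in migraine days and change the answer labels to match the stem.

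**Consistency corrections in the same edit.**
- In the synopsis, replace the 3-item screen with the AMPP/AMS module used in Sections 6 and 6.1 and screener item 7.
- In screener item 1, add family members of employees, to match Section 6.2.

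**Cost.** A few lines of protocol and screener text, with no added items and no real burden on participants. Under Section 10.1 an amendment needs ethics approval before it takes effect, so the edit is cheapest before the screener goes live.
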